##### **Inclusion criteria**

- Patients who experienced LR as first event of recurrence after treatment for localized high-grade osteosarcoma of bone, including cases with synchronous lung metastases
- Adequate patient compliance to follow-up visits
- Written informed consent prior to any study-specific analysis and/or data collection
- No age limits

##### **Exclusion criteria**

- Cases of LR demonstrated after > 3 months after metastatic disease
- Impossibility to ensure adequate compliance

#### **5. Retrospective observational analysis and data collection**

Together with the prospective observational study, a retrospective analysis including all the cases with a histological diagnosis of localized high-grade osteosarcoma who experienced LR as first event of recurrence after treatment from 01 Jan 1980 to 31 Dec 2021 will be performed.

The data will be extracted retrospectively from prospectively maintained institutional database and will be checked through a revision of patient records.

The following data will be collected:

- demographics (gender, date of birth, age at diagnosis),

- disease characteristics (morphological subtype, dimension, primary site),
- treatment received (date of surgery, surgical margins, radiation therapy, timing of radiation therapy, chemotherapy, timing of chemotherapy, type of regimen used, best response according to RECIST 1.1)
- date of LR, modality of LR diagnosis, clinical suspect or imaging, presence, or absence of DM at LR diagnosis, type of treatment after LR, date of surgical complete remission after LR (CR2), surgical margins
- outcome (recurrence type and timing, patient status at last follow-up)

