## **3. STUDY DESIGN**

This is a multicenter retrospective and prospective study that will analyze all cases with of

diagnosis of LR in high-grade osteosarcoma from 01 January 1980 and all new cases referring to each participant site.

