### Inclusion criteria

- Male and female patients treated for localized high-grade osteosarcoma from 01 Jan 1980 to 31 Dec 2021.
- Clinical Information available
- No age limits

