## **10. Informed consent**

All Patients will be informed, by the investigator, of the aims of the study, the possible risks and benefits that will derive from the study participation.

The Investigator must clearly inform that the patient is free to refuse participation in the

study and that can withdraw consent at any time and for any reason.

They will be informed as to the strict confidentiality of their patient data, but that their medical records may be reviewed for trial purposes by authorized individuals other than their treating physician.

The informed consent procedure must conform to the ICH guidelines on Good Clinical Practice. This implies that "the written informed consent form should be signed and personally dated by the patient or by the patient's legally acceptable representative".

The Investigator must also sign the Informed Consent form and will keep the original at the site and a copy of the original must be handed to the patient.

The competent ethics committee for each Institution participating to the study must validate local informed consent documents before the study can be opened. It will be emphasized that the participation is voluntary and that the patient is allowed to refuse further participation in the study whenever he/she wants. This will not prejudice the patient's subsequent care.

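### The retrospective window is dated in conflicting ways and ends on a fixed day not tied to each site's prospective start, so some early post-LR deaths may fall in neither part and other patients may qualify for both

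*Protocol*

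**What the plan says.** The retrospective window is stated in three places.

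- Section 3 (Study design) covers cases with "diagnosis of LR in high-grade osteosarcoma from 01 January 1980 and all new cases referring to each participant site". The date attaches to the LR diagnosis, and there is no closing date.
- Section 5 covers cases "who experienced LR as first event of recurrence after treatment from 01 Jan 1980 to 31 Dec 2021 will be performed". Grammatically the dates can belong to the LR or to the treatment.
- The section 5.1 inclusion criterion reads "Male and female patients treated for localized high-grade osteosarcoma from 01 Jan 1980 to 31 Dec 2021". Here the dates belong to treatment of the primary.

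The prospective part has no calendar start. The section 4.1 criteria require "Written informed consent prior to any study-specific analysis and/or data collection" and "Adequate patient compliance to follow-up visits". They define the population as "Patients who experienced LR as first event of recurrence after treatment for localized high-grade osteosarcoma of bone", with no limit on the LR date. Section 9 requires approval before the study is initiated, and section 10 says: "The competent ethics committee for each Institution participating to the study must validate local informed consent documents before the study can be opened".

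Section 7 foresees that some eligible subjects will have died. It gives no rule for cases that fall between the two parts. The primary objective in section 2 is PLRS.

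**The concern.** One common end date for the retrospective part can meet the opening dates of several sites only by coincidence. Where a site opens later, there is an interval in which a relapsed patient can be reached only through the prospective route. That requires the patient to be alive, to consent and to be able to attend follow-up. Entry then depends on the primary outcome: those who die soon after LR drop out and those who live longer stay in. The error in PLRS runs upward, and it falls on the most recent patients.

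The conflict over which date defines the window matters because it decides who is lost. It also creates the reverse problem. If the dates refer to treatment, a patient treated by 31 Dec 2021 who relapses after the site opens meets both sets of criteria, and no rule assigns that patient to one part.

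**Working it through.** The protocol states no PLRS rate, opening date or bias, so there is no figure of its own to reproduce. The check has two steps: who is eligible under each reading, and how many could be lost.

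**Step 1. Eligibility if a site opens G months after 31 Dec 2021**

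| Patient | LR-date reading | Treatment-date reading |
|---|---|---|
| Treated by 2021, LR in the gap, dies before opening | in neither part | retrospective |
| Treated after 2021, LR in the gap, dies before opening | in neither part | in neither part |
| LR in the gap, alive at opening | prospective, if consenting and compliant | prospective; also retrospective if treated by 2021 |
| Treated by 2021, LR after opening | prospective | qualifies for both |

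On the treatment-date reading with opening within 24 months, every lost patient has a local relapse-free interval (LRFI) under 24 months. All therefore fall on the early side of the early/late LR split in section 2.

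**Step 2a. Loss on the LR-date reading**

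Inputs from the protocol: about 50 prospective patients in 36 months (section 4.1), so 50/36 = 1.39 per month; about 100 retrospective patients (section 5.1) over 42 years, so 100/42 = 2.4 per year. Assumptions: LR arrives uniformly; PLRS is exponential with median m of 12, 24 or 36 months; G is 6, 12 or 24 months.

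With λ = ln 2 / m:

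- share dead before opening: d = 1 − (1 − exp(−λG)) / (λG)
- patients lost: 1.39 × G × d
- true 24-month PLRS: S = exp(−24λ)
- 24-month PLRS among gap survivors, counted from LR without late-entry adjustment: S / (1 − d), valid for G ≤ 24
- pooled estimate, with k surviving gap patients added to 100 + 50 others: (150·S + k·S/(1 − d)) / (150 + k)

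| m | G | d | LR in gap | lost | true S | gap survivors | pooled bias (points) |
|---|---|---|---|---|---|---|---|
| 12 | 6 | 15% | 8.3 | 1.3 | 0.250 | 0.296 | 0.2 |
| 12 | 12 | 28% | 16.7 | 4.6 | 0.250 | 0.347 | 0.7 |
| 12 | 24 | 46% | 33.3 | 15.3 | 0.250 | 0.462 | 2.3 |
| 24 | 6 | 8% | 8.3 | 0.7 | 0.500 | 0.545 | 0.2 |
| 24 | 12 | 15% | 16.7 | 2.6 | 0.500 | 0.592 | 0.8 |
| 24 | 24 | 28% | 33.3 | 9.3 | 0.500 | 0.693 | 2.7 |
| 36 | 6 | 6% | 8.3 | 0.5 | 0.630 | 0.667 | 0.2 |
| 36 | 12 | 11% | 16.7 | 1.8 | 0.630 | 0.706 | 0.7 |
| 36 | 24 | 20% | 33.3 | 6.6 | 0.630 | 0.787 | 2.4 |

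Example, m = G = 24: k = 33.3 − 9.3 = 24.0, and (150 × 0.500 + 24.0 × 0.693) / 174.0 = 0.527, which is 2.7 points too high.

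At 2.4 cases per year the worst cell holds 2.4 × 2 = 4.8 gap cases and loses 4.8 × 0.46 = 2.2.

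**Step 2b. Loss on the treatment-date reading**

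A lost patient must be treated, relapse and die, all within the gap. Assume LRFI is also exponential, with median 12 or 24 months (rate a), and PLRS has rate b. The number lost is r × ∫₀ᴳ F(t) dt, where r is the monthly rate and F is the distribution function of LRFI plus PLRS. For a ≠ b the integral is G − [b(1 − exp(−aG))/a − a(1 − exp(−bG))/b] / (b − a). For a = b = λ it is G − 2/λ + exp(−λG)(G + 2/λ).

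With both medians 12 and G = 24: 24 − 34.6 + 0.25 × (24 + 34.6) = 4.03, times 1.39 = 5.6 patients. Over PLRS medians of 12 to 36 months, the loss is below 0.2 for G = 6, 0.2 to 1.0 for G = 12 and 1.3 to 5.6 for G = 24. At 2.4 cases per year it is below 1 throughout.

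**The case against.** A reader might infer that everyone who relapses after 31 Dec 2021 and dies before opening is excluded. The documents do not support that. The only formal retrospective eligibility criterion, in section 5.1, dates the window by treatment, and section 3 sets no end date. Under section 5.1 most of these patients stay eligible retrospectively. This objection stands, and it is why the loss is stated separately for each reading.

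A reader might also infer that PLRS is materially overstated. That is not shown. No opening date is given, so the gap length is unknown; if a site had opened by 31 Dec 2021, there would be overlap and no gap. The rate of 50 in 36 months is an enrolment target, not an LR incidence, and may include living patients with older relapses. With about 150 patients the standard error of a survival proportion near 50% is √(0.5 × 0.5 / 150), about 4 points, which exceeds every pooled bias in the table. The planned analysis is descriptive, and no PLRS for a recent period is a stated objective. All of this stands as a limit on size.

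An analysis that counts survivors at risk only from consent could in principle remove the upward bias among them, and an SAP may provide for it. It cannot restore the missing cases to the description of diagnosis, pattern and treatment of LR, or make good the full coverage claimed in section 3.

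Section 7's remark on deceased subjects does not close the gap. It follows the paragraph on retrospective extraction and does not extend any date.

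**Conclusion.** The point holds in a limited form. Sections 3, 5 and 5.1 do not agree on the date that defines the retrospective window, and its fixed end is not linked to the site-specific, consent-dependent opening of the prospective part. The two parts therefore cannot be relied on to meet. Where a gap exists, the loss is selective and pushes PLRS upward. Where the treatment-date reading applies, the loss is smaller and double eligibility appears.

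The size cannot be fixed from the documents. The LR-date range of about 0.5 to 15 patients, and the pooled bias of about 0.2 to 2.7 points at 24 months, rest on assumed PLRS medians, assumed gap lengths, the target rate of 50 per 36 months and no late-entry adjustment. At the historical rate at most about 2 patients are lost, and on the treatment-date reading fewer still. The pooled effect is small unless the gap is long. The reason to act is that the defect touches the primary objective, is one of eligibility and is cheap to remove.

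**What to change.** In sections 5 and 5.1, define the retrospective window by date of LR diagnosis, from 01 Jan 1980 to the day before activation of each site, and align section 3 with this. State that deceased patients are included as far as ethics approval allows. This needs saying because section 5.1 lists no consent criterion while section 7 opens with written consent, so whether the retrospective route is free of consent is not stated. Enter patients with LR on or after activation prospectively, and count each patient once.

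Moving only the end date is not enough. A treatment-date window running to activation would still admit patients treated before activation who relapse afterwards, and they would qualify for both parts.

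The cost is a few changed phrases and a short extra chart extraction per site. A few recent patients will have only the retrospective data list.

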## 5.1 Study population

Through the collaboration of the joining institutions, we plan to include approximately 100 patients

### Inclusion criteria

- Male and female patients treated for localized high-grade osteosarcoma from 01 Jan 1980 to 31 Dec 2021.
- Clinical Information available
- No age limits

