#### **4. Prospective observational analysis and data collection**

Clinical data will be retrieved by patient charts.

A protocol-specific CRF reporting the results of the review will be provided.

Data from all patients diagnosed with OS will be prospectively entered in this platform.

Each patient will be provided with an informational leaflet for his/her general practitioner and asked to sign an informed consent prior to data entry.

The following information will be recorded in the database:

- Demographics – patient name, DOB, gender, date of first consultation, data of diagnosis
- Data on primary tumor – size, site, evidence of multifocality
- Data on histological diagnosis – morphology (classical type, proximal type, mixed), mitotic count, depth
- Data on staging at diagnosis – evidence of lymph-nodal and/or distant metastases
- Data on treatment of primary tumor – surgery, radiotherapy, chemotherapy
- Data on recurrence – type of recurrence, site, date
- Data on treatment of local relapse – surgery, radiotherapy, chemotherapy
- Data on treatment of metastatic disease – pulmonary metastasectomy, radiotherapy
- Data on chemotherapy for metastatic disease – line, regimen, number of cycles, best response, duration of response
- Patient status at last follow-up (dead of disease, DOD, alive with disease, AWD, nonevidence of disease, NED)

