### Exclusion criteria

- Cases of LR demonstrated after > 3 months after metastatic disease
- Evidence of metastatic disease at presentation

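### The protocol defines the retrospective and prospective populations on different date anchors, so some patients meet both lists and no rule assigns them to one cohort

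*Protocol*

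**What the plan says.** Four places in the Protocol say who is in the study.

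- **Section 3 (Study design)** covers all cases with a "diagnosis of LR in high-grade osteosarcoma from 01 January 1980 and all new cases referring to each participant site". The anchor is the diagnosis of LR, with a start date and no end date.
- **Section 5 (retrospective, lead-in)** covers localized high-grade cases "who experienced LR as first event of recurrence after treatment from 01 Jan 1980 to 31 Dec 2021 will be performed". LR as first event is required. The dates can attach to the relapse or to the treatment.
- **Section 5.1 (retrospective inclusion list)** reads "Male and female patients treated for localized high-grade osteosarcoma from 01 Jan 1980 to 31 Dec 2021". The anchor is primary treatment. The only other entries are available clinical information and the absence of an age limit. LR is not listed.
- **Section 4.1 (prospective inclusion list)** reads "Patients who experienced LR as first event of recurrence after treatment for localized high-grade osteosarcoma of bone, including cases with synchronous lung metastases". LR as first event is required, with no date for the relapse or for primary treatment. This list also asks for written consent before data collection and for adequate compliance with follow-up.

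Both cohorts exclude "Cases of LR demonstrated after > 3 months after metastatic disease". Section 4 adds a broader sentence: "Data from all patients diagnosed with OS will be prospectively entered in this platform". The planned sizes are about 50 prospective patients in 36 months (Section 4.1) and about 100 retrospective patients (Section 5.1).

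**The concern.** The primary objective is post-LR survival, whose clock starts at LR. The natural boundary between the cohorts is therefore the date of first LR, but the operative retrospective list uses the date of primary treatment. LR follows treatment after a lag; Section 2 itself separates early relapses (1 to 24 months) from late ones (beyond 24 months). Patients treated before the cut-off will therefore go on relapsing after it, and these are the patients who fit both lists.

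The two routes filter differently. A prospective patient must be alive and willing to sign, and must be judged likely to comply with follow-up. The retrospective list has no such entries, and Section 7 expects some eligible subjects to have died. Consent and compliance both act on survival, so the route by which a patient enters can change which survival times are observed. A descriptive analysis is not immune, because a descriptive survival estimate depends on who is in it.

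**Working it through.** **Step 1. Put test patients through the four definitions.**

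| Patient | Section 3 | Section 5 | Section 5.1 list | Section 4.1 list |
|---|---|---|---|---|
| A: primary treated 2020, first LR 2023, consents and complies | in | in if the dates mean treatment, out if they mean LR | in | in |
| B: primary treated before 1980, first LR after 1 Jan 1980 but before 2022 | in | out if the dates mean treatment, in if they mean LR | out | in only if alive, consenting and compliant |
| C: primary treated and first LR both between 1980 and 2021, alive, consenting and compliant | in | in | in | in |

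All three are taken to have had localized disease with LR as first event. Patient A meets both lists, and no section says which cohort takes precedence. Patient B is inside Section 3 and outside 5.1. Patient C also meets the listed prospective criteria because 4.1 has no start date for LR; only the mention of new cases in Section 3 points the other way.

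The overlap arises from the treatment-date anchor in 5.1 combined with the missing date in 4.1. The absent LR entry in 5.1 does not cause it, since anyone who also meets 4.1 has had LR.

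**Step 2. Illustrate the size of the type A overlap.** The protocol gives no figure to reproduce.

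Inputs from the protocol: cut-off 31 Dec 2021, 50 prospective patients, 36 months of accrual. Assumptions, not in the protocol: steady LR incidence; an LR-free interval that is exponential with mean *m* years; prospective accrual starting *s* years after the cut-off.

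For an LR occurring *t* years after the cut-off, the chance that the primary was treated before the cut-off is exp(−t/m). Averaged over three years of accrual:

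share = (1/3) × ∫ from s to s+3 of exp(−t/m) dt = (m/3) × exp(−s/m) × [1 − exp(−3/m)]

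For s = 0:

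- m = 1: (1/3)(1 − 0.050) = 0.317, × 50 = 16
- m = 1.5: 0.5 × (1 − 0.135) = 0.432, × 50 = 22
- m = 2: (2/3)(1 − 0.223) = 0.518, × 50 = 26
- m = 3: 1 × (1 − 0.368) = 0.632, × 50 = 32

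A later start multiplies each share by exp(−s/m):

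| Start of accrual | m = 1 | m = 3 |
|---|---|---|
| at cut-off (s = 0) | 0.317, about 16 of 50 | 0.632, about 32 of 50 |
| one year later (s = 1) | 0.317 × 0.368 = 0.117, about 6 | 0.632 × 0.717 = 0.453, about 23 |
| two years later (s = 2) | 0.317 × 0.135 = 0.043, about 2 | 0.632 × 0.513 = 0.325, about 16 |

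**Step 3. Ask whether an LR-date cut at 31 Dec 2021 is enough.** It would remove the dual eligibility. But if prospective enrolment starts later, a patient who relapses between the two dates is too late for the retrospective cohort and enters the prospective one only if still alive to consent. Those who die in the gap appear in neither cohort, which biases post-LR survival upwards.

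**The case against.** The strongest reply is that the intended population is clear. The Section 5 lead-in requires LR as first event, Section 3 speaks of LR cases, the Section 5 data list collects the date and treatment of LR, and the exclusion criterion presupposes LR. The size target agrees: "we plan to include approximately 100 patients", whereas at the 4% to 10% LR rate in the Background, 100 patients selected on 5.1 alone would include only about 4 to 10 with LR. This stands. A reader might infer from 5.1 that patients without LR are to be enrolled; the documents do not support that, and the missing entry is an internal inconsistency.

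The overlap counts depend on an assumed interval distribution and start date. If the Section 5 dates mean LR and override 5.1, and new cases in Section 3 define the prospective cohort, the overlap is zero. That also stands: the counts show only that the overlap need not be marginal.

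The consent contrast is less sharp than the two lists suggest. Section 7 opens with a consent sentence not limited to one cohort, and Section 10 addresses all patients; Section 7 then describes retrospective selection separately. Retrospective consent is therefore unclear, not plainly waived. The compliance difference remains.

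A reader might also infer that patients will be counted twice, or that sites will pick a route once the outcome is known. Neither is shown. Section 8 asks for a CRF per included subject, and Section 12 requires a coded identifier with a site register, so duplicates within a site can be detected. Finally, the Section 4 sentence describes what is entered in a data platform and is loose wording more than a rival eligibility rule.

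None of this says which anchor governs or which cohort takes patient A.

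**Conclusion.** The point holds as an inconsistency in the eligibility text. Sections 3, 5, 5.1 and 4.1 use different or undetermined date anchors, 5.1 omits a requirement stated in its own section lead-in, and a patient treated by 31 Dec 2021 with a later first LR meets both lists without being assigned to either. Because the lists differ on compliance, and on consent as far as the text can be read, assignment can affect who contributes to post-LR survival.

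The textual conflict is certain; its numerical effect is not known. The illustrative range of 2 to 32 of 50 rests on steady incidence, an exponential interval of mean 1 to 3 years, and a start between zero and two years after the cut-off, none of which the protocol states. No bias in the survival estimate has been quantified. The wording should be corrected because eligibility belongs in the protocol and the correction is cheap.

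**What to change.** 1. Use the date of first LR as the only anchor in Sections 3, 4.1, 5 and 5.1, with explicit start and end dates for each cohort.
2. Add LR as first event of recurrence to the 5.1 inclusion list.
3. State that each patient belongs to one cohort only, determined by the date of first LR.
4. Align the Section 4 sentence on prospective data entry with the LR requirement in 4.1.
5. Deal with survivor selection. Either set the boundary so that no LR falls between the retrospective cut-off and the start of prospective enrolment, or count prospective patients as at risk only from consent (delayed entry, with LR kept as time origin). Delayed entry also covers the lag from LR to signature within the prospective cohort.
6. Say in Section 7 whether written consent applies to retrospective patients and how deceased patients are handled.

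The cost is a few lines of protocol text. No extra patients are needed, and the only added data item is the consent date in the analysis file if delayed entry is used.

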### Exclusion criteria

- Cases of LR demonstrated after > 3 months after metastatic disease
- Evidence of metastatic disease at presentation

